12.6.3 Analysis of the secondary endpoints

Analysis of all secondary endpoints will be performed in the ITT population. Summary statistics and frequency tables will be provided for all secondary endpoints by visit and treatment.

Proportions of patients having HbA1c target values of $\leq 6.5\%$ and $<7.0\%$ at Visit 7 (Week 24), Visit 10 (Week 52), and at each intermediate visit will be compared between treatments using the CMH procedure, in which baseline HbA1c strata will serve as the stratification factors. Any ITT patient who only has baseline HbA1c value but no post-baseline HbA1c value will be considered as not achieving HbA1c goal at endpoint.

As a supportive analysis, the probabilities of patients reaching HbA1c targets of $\leq 6.5\%$ and $<7.0\%$ will also be analyzed using a logistic regression model. The independent variables will include treatment group, HbA1c baseline strata ($<9.0\%$ or $\geq 9.0\%$), and country as factors, and baseline HbA1c as a continuous covariate.

The same CMH procedure and logistic regression as described above will be used to analyze data on proportion of patients discontinuing the study, needing rescue due to failure to maintain glycemic control. However, the number of rescue episodes at Visit 7 (Week 24), Visit 10 (Week 52), and at each intermediate visit will be analyzed in an exploratory fashion, using descriptive statistics only.

The effects of the study medications on the homeostatic model assessment (HOMA) will be examined. The pancreatic beta-cell function (% HOMA-B) and peripheral and hepatic insulin sensitivity (% HOMA-S) will be computed from a computerized HOMA model, which can predict the plasma glucose, insulin, C-peptide, and proinsulin concentrations for any possible combination of these 2 parameters in the fasting state in patients not taking insulin.

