2.1.4 Evaluable analysis set

The Evaluable analysis set will consist of all randomized patients who receive at least 1 dose of randomized study medication and have at least 1 baseline and post-baseline HbA1c assessment. Evaluable patients will be analyzed in accordance to their planned treatment group.

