Secondary 2	Evaluable	Proportions of patients having HbA1c goals of <6.5%, ≤6.5% and <7.0% at Week 24 and at each intermediate visit	assumption of MMRM analysis. Rescue and IP discontinuation: Data after event excluded. Composite approach used, with patients with missing data at endpoint treated as non-responders. Withdrawal from study prior to Week 24: Composite approach used, with patients with missing data at endpoint treated as non-responders.	Difference in proportion of responders at Week 24 and each intermediate visit between EQW and PBO
Sensitivity to secondary 2	Evaluable	Proportions of patients having HbA1c goals of <6.5%, ≤6.5% and <7.0% at Week 24 and at each intermediate visit	Rescue and IP discontinuation: Data after event excluded. Hypothetical approach using MI pattern mixture model imputation. Withdrawal from study prior to Week 24: Hypothetical approach using MI pattern mixture model imputation.	Difference in proportion of responders at Week 24 and each intermediate visit between EQW and PBO
Other continuous secondary endpoints	ITT	Change in X from baseline to Week 24 and each intermediate visit	Rescue and IP discontinuation: Data after event excluded. Hypothetical approach due to MAR	Least squares mean difference in CFBL at Week 24 and each intermediate visit, as applicable.

				assumption of MMRM analysis. Withdrawal from study prior to Week 24: Hypothetical approach due to MAR assumption of MMRM analysis.	
Exploratory	Safety	Change in eGFR from baseline to Week 24 and each intermediate visit by baseline eGFR category	Rescue and IP discontinuation: Data after event excluded. Hypothetical approach due to MAR assumption of MMRM analysis. Withdrawal from study prior to Week 24: Hypothetical approach due to MAR assumption of MMRM analysis.	Least squares mean difference in CFBL at Week 24 and each intermediate visit.	
Sensitivity to exploratory	Safety	Change in eGFR from baseline to Week 24 and each intermediate visit by baseline eGFR category	Rescue: Data after event included. Treatment policy approach. IP discontinuation: Data after event excluded. Hypothetical approach due to MAR assumption of MMRM analysis.	Least squares mean difference in CFBL at Week 24 and each intermediate visit.	

				Withdrawal from study prior to Week 24: Hypothetical approach due to MAR assumption of MMRM analysis.	
--	--	--	--	-------------------------------------------------------------------------------------------------------	--

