4.2.3.5 Analysis of secondary variables

Summary statistics and frequency tables will be provided for all secondary endpoints by visit and treatment for the ITT analysis set during the controlled assessment period and separately for the subset of ITT patients who received open-label EQW during the extension period for the Treatment period (see Section 3.6.5 for Treatment period definition), unless otherwise stated.

Similar to the primary analysis, data including the Early Termination visit where applicable will be included in the MMRM and CMH analysis for secondary analysis variables. Data collected from an Early Termination visit will be mapped to the next closest scheduled visit. For patients who initiate rescue medication and continue study participation, data collected after the initiation of rescue medication will be excluded from analyses. Data collected after discontinuation of IP will be excluded from analyses for all secondary efficacy endpoints.

Change in HbA1c from baseline Visit 2 (Week 0) to Visit 10 (Week 52), and to each intermediate visit as applicable

The MMRM method for change in HbA1c will be used until Week 24 and to each intermediate visit, using the Evaluable analysis set, which is the same approach as stated in Section 4.2.3.3.

The least squares mean (LSM) change from baseline and SE bar by visit will be presented in a figure by treatment group. The p-value for the difference between treatment groups by visit will also be provided in the figure.

The observed values and change from baseline will be summarized by visit using descriptive statistics (mean, median, standard deviation, minimum, maximum). This will be provided separately for both the Evaluable analysis set during the controlled assessment period and for the subset of Evaluable patients who received open-label EQW during the extension period analysis set for the Treatment period.

HbA1c measures will be listed.

Change in fasting plasma glucose concentration, body weight, fasting insulin, lipids, blood pressure from baseline Visit 2 (Week 0) to Visit 7 (Week 24), Visit 10 (Week 52), and to each intermediate visit as applicable

The same MMRM approach will be used to analyze the change in body weight, blood pressure, fasting plasma glucose, and fasting insulin from baseline (Week 0) to Week 24, and each intermediate visit.

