The least squares mean (LSM) change from baseline and SE bar by visit will be presented in a figure by treatment group. The p-value for the difference between treatment groups by visit will also be provided in the figure.

The observed values and change from baseline will be summarized by visit using descriptive statistics (mean, median, standard deviation, minimum, maximum) for body weight, blood pressure, fasting plasma glucose, fasting insulin and lipids. This will be provided separately for both the ITT analysis set during the controlled assessment period and for the subset of ITT patients who received open-label EQW during the extension period for the Treatment period.

The models for changes in body weight, blood pressure, fasting plasma glucose, and fasting insulin will include treatment group, visit, interaction between visit and treatment, region, baseline of the dependent variable, interaction between visit and baseline of the dependent variable and screening HbA1c strata ($<9.0\%$, $\geq 9.0\%$) as the fixed effects. The REML method will be used for parameter estimation. The least squares mean, 2-sided 95% confidence interval, and p-value of the difference in the endpoints of interests between the EQW and PBO groups will be provided.

FPG, body weight, fasting insulin, lipids and blood pressure (systolic and diastolic) will be presented in listings.

Proportions of patients achieving HbA1c goals at Visit 7 (Week 24), Visit 10 (Week 52), and at each intermediate visit

Proportions of patients having HbA1c goals of $<6.5\%$, $\leq 6.5\%$ and $<7.0\%$ at Week 24 and at each intermediate visit will be compared between treatments using the Evaluable analysis set via the CMH procedure, in which screening HbA1c strata ($<9.0\%$, $\geq 9.0\%$) will serve as the stratification factors.

A bar chart of the percentage of patients achieving HbA1c goals of $<6.5\%$, $\leq 6.5\%$ and $<7.0\%$ by visit and treatment group will be provided along with p-values.

Any Evaluable patient without HbA1c value at the endpoint will be considered as not achieving HbA1c goal at endpoint. The denominator will be the total number of Evaluable patients in a treatment group, and the numerator will be the number of patients achieving HbA1c $<6.5\%$, $\leq 6.5\%$ and $<7.0\%$.

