As a sensitivity analysis also in the Evaluable analysis set, the probabilities of patients reaching HbA1c targets of $<6.5\%$, $\leq 6.5\%$ and $<7.0\%$ will be analyzed to Week 24 using the CMH procedure, with missing data imputed using MI pattern mixture model imputation. HbA1c strata ($<9.0\%$, $\geq 9.0\%$) will serve as the stratification factors. The imputed HbA1c data for the sensitivity analysis of the primary endpoint (Section 4.2.3.4) will be used for this analysis.

The number and percentage of patients having HbA1c target values of $<6.5\%$, $\leq 6.5\%$ and $<7.0\%$ will be summarized by visit and treatment group. This will be provided separately for both the Evaluable analysis set during the controlled assessment period and for the subset of Evaluable patients who received open-label EQW during the extension period for the Treatment period.

Proportions of patients discontinuing the study, needing rescue due to failure to maintain glycemic control, and number of rescue episodes at Visit 7 (Week 24), Visit 10 (Week 52), and at each intermediate visit

A Kaplan-Meier table and corresponding figure of time to rescue will be provided. Patients who are not rescued will be censored at Week 24 visit or last dose of study medication for those who discontinue study treatment for reasons unrelated to lack of glycemic control, as indicated by an adverse event withdrawal that required rescue medication prior to Week 24 visit.

The number and percentage of patients needing rescue due to failure to maintain glycemic control will be summarized by visit according to the windows defined in Section 4.3.1. This will be provided separately for both the ITT analysis set during the controlled assessment period and for the subset of ITT patients who received open-label EQW during the extension period for the Treatment period. The number of patients included at each analysis visit will be derived by including patients in the counts at every visit up to study completion date or date of last dose of study medication for patients who prematurely discontinue study medication.

Data collected after study treatment discontinuation will be excluded from summaries.

The proportion of patients discontinuing the study will be presented in the disposition table, by study period.

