CSP Section 12.6.1 states that last observation carried forward will be used for missing data at endpoint for proportion of patients meeting HbA1c goals of $\leq 6.5\%$ and $< 7.0\%$, however, patients with missing HbA1c at endpoint will be considered as non-responders. Additionally, the logistic regression sensitivity analysis described in the CSP has been replaced with a more appropriate CMH analysis using MI pattern mixture model imputation (Sections 4.2.3.4 and 4.2.3.5), as this tests the robustness of the results from the main analysis by altering the missing data assumption.

CSP Section 12.6.1 stipulates ‘The analyses of all other efficacy endpoints will be performed in ITT population.’ Upon review of the endpoints it was agreed that all endpoints related to HbA1c should be evaluated using the Evaluable analysis set.

CSP Section 12.6.1 outlines a MMRM method will be implemented for the secondary efficacy endpoint, lipids. It was agreed after blinded data review that the data could be sufficiently reviewed as summary statistics.

CSP Section 12.6.2 specifies that both baseline HbA1c and HbA1c strata will be included in the MMRM model for the primary analysis. However, these variables will be highly correlated resulting in multicollinearity in the statistical model. Therefore, HbA1c strata will not be included in the primary model. For secondary and exploratory MMRM analyses, screening HbA1c strata will be used in the model instead of continuous baseline HbA1c.

The sensitivity and supportive analyses in Section 4.2.3.4 were not specified in the CSP and have been added to further support the primary analysis and to examine the influence of missing data due to drop-out and/or receiving rescue therapy.

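### The HbA1c-goal analysis drops dosed patients with no post-baseline HbA1c, whom the protocol counts as failures, and SAP section 5 does not say so

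*SAP*

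**What the plan says.** Protocol 12.6.3 analyses the secondary endpoints in the ITT population (randomised and dosed) and has an explicit rule for patients with no follow-up value: "Any ITT patient who only has baseline HbA1c value but no post-baseline HbA1c value will be considered as not achieving HbA1c goal at endpoint".

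The SAP moves this endpoint to the Evaluable set, whose members must be dosed and "have at least 1 baseline and post-baseline HbA1c assessment" (SAP 2.1.4). In SAP 4.2.3.5 the CMH comparison is run in that set, the failure rule is limited to it ("Any Evaluable patient without HbA1c value at the endpoint will be considered as not achieving HbA1c goal at endpoint"), and so is the denominator: "The denominator will be the total number of Evaluable patients in a treatment group". The multiple-imputation analysis of the same endpoint is placed there too: "As a sensitivity analysis also in the Evaluable analysis set". Table 2 in SAP 4.2.3.1 agrees. Its entry Secondary 2 has the Evaluable population and this handling of withdrawal before Week 24: "Composite approach used, with patients with missing data at endpoint treated as non-responders".

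SAP section 5 declares two relevant changes, both referenced to protocol 12.6.1. Non-response replaces last observation carried forward, and "it was agreed that all endpoints related to HbA1c should be evaluated using the Evaluable analysis set". It does not mention the protocol 12.6.3 rule. SAP 4.1.3.1 states the failure rule for patients with a missing Week 24 value without restricting it to the Evaluable set.

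**The concern.** A change-from-baseline MMRM cannot use a patient with no post-baseline value, so the Evaluable restriction is understandable for the primary endpoint. A responder analysis that scores missing as failure has no such need. Restricting it is a post-randomisation exclusion with no analytic purpose. It removes the earliest losses, which the composite strategy in Table 2 would otherwise score as failures.

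Each exclusion raises the observed response rate in the arm that loses the patient, so the treatment difference can move either way. A reader of SAP section 5 and SAP 4.1.3.1 would also conclude that these patients are still counted as failures, when SAP 4.2.3.5 removes them.

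**Working it through.** **Set logic.** Consider a patient who is randomised, dosed, has a baseline HbA1c and gives no later HbA1c.

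| Source | Handling |
|---|---|
| Protocol 12.6.3 | In ITT; counted as not reaching the goal |
| SAP 4.1.3.1 (general rule) | Reads as a failure |
| SAP 2.1.4 | Not Evaluable |
| SAP 4.2.3.5, CMH analysis | In neither numerator nor denominator |
| SAP 4.2.3.5, imputation analysis and visit summaries | Same set, so absent |

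**Consistency between similar patients.** Two patients stop study drug before Week 4. One attends the Early Termination visit and gives an HbA1c sample. If that sample makes the patient Evaluable, the patient counts as a failure at Week 24. The sample is either excluded ("Data collected after discontinuation of IP will be excluded from analyses for all secondary efficacy endpoints") or falls in the day 2 to 42 window for Week 4 (SAP Table 3.1), so there is no Week 24 value. The other gives no sample and leaves the analysis. Neither has endpoint data.

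**The plan's own figure.** The documents give no power or sample size for the goal endpoint. The stated 74% is for the primary endpoint. With 50 and 20 patients, difference 0.7, SD 1.0 and two-sided 0.05, a noncentral t calculation gives 74.2%, so it reproduces, but it does not bear on this point.

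**Size of the effect.** Arm sizes come from 77 patients at 5:2: 77 × 5/7 = 55 EQW and 77 × 2/7 = 22 placebo. Responder counts and numbers excluded are not in the documents and are assumed: 22 EQW and 4 placebo responders.

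- ITT rates: 22/55 = 40.0% and 4/22 = 18.2%; difference 21.8 points.
- Standard error: √(0.400 × 0.600/55 + 0.182 × 0.818/22) = 10.5 points.
- Dropping k non-responders from an arm of n multiplies its rate by n/(n − k).
- Unstratified Mantel-Haenszel test, for illustration only: χ² = (x₁ − n₁m/N)² / [n₁n₂m(N − m)/(N²(N − 1))], where x₁ is EQW responders, m all responders and N all patients. For ITT, x₁ = 22, n₁ = 55, n₂ = 22, m = 26 and N = 77, so χ² = 3.30.

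| Excluded | EQW | Placebo | Difference | Shift | p |
|---|---|---|---|---|---|
| None (ITT) | 22/55 = 40.0% | 4/22 = 18.2% | 21.8 | – | 0.069 |
| 1 EQW | 22/54 = 40.7% | 18.2% | 22.6 | +0.7 | 0.062 |
| 1 placebo | 40.0% | 4/21 = 19.0% | 21.0 | −0.9 | 0.087 |
| 1 in each arm | 40.7% | 19.0% | 21.7 | −0.1 | 0.078 |
| 2 EQW, 1 placebo | 22/53 = 41.5% | 19.0% | 22.5 | +0.6 | 0.070 |
| 3 EQW | 22/52 = 42.3% | 18.2% | 24.1 | +2.3 | 0.048 |

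Range over the assumed response rates, one patient excluded:
- EQW, 16 to 28 responders of 55 (29% to 51%): 16/54 − 16/55 = +0.5 points, up to 28/54 − 28/55 = +0.9.
- Placebo, 2 to 7 responders of 22 (9% to 32%): the placebo rate rises by 2/21 − 2/22 = 0.4 points, up to 7/21 − 7/22 = 1.5, so the difference falls by the same amount.

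**The case against.** The strongest reply concerns weight. The new set, its definition and the non-responder rule are all declared in SAP section 5, so the lost rule can be deduced from them. The text specific to the endpoint (Table 2 and SAP 4.2.3.5) is consistent, and a programmer following it faces no ambiguity. The protocol rule was written beside last observation carried forward, which did not carry Week 0 values forward and so needed a rule for baseline-only patients. For every Evaluable dropout the SAP is now stricter than the protocol. The affected group may be empty, because HbA1c is taken at Week 4 and patients who stop drug are invited to an Early Termination visit that includes it. The endpoint lies outside the testing hierarchy, and set sizes by arm will be reported anyway.

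All of that stands, and it makes this a matter of incomplete disclosure and an avoidable exclusion, not a hidden change. It does not explain why a missing-equals-failure analysis should leave anyone out.

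Three narrower points:
- SAP 2.1.4 does not say whether an Early Termination sample later excluded from analysis still confers Evaluable status, so the two-patient comparison depends on that reading.
- If the main analysis moves to ITT while the imputation analysis stays in Evaluable, the two differ in population as well as in missing-data assumption. This can be handled (see the fix).
- A patient without a baseline value could be non-Evaluable and yet a responder. This case is practically empty, because a screening HbA1c is required for entry (protocol 4.2) and can serve as baseline (SAP 3.6.1).

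**Conclusion.** The concern holds. A dosed patient with no post-baseline HbA1c is in no planned goal analysis, protocol 12.6.3 counts that patient as a failure, and SAP section 5 does not say that this rule lapses.

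The numerical consequence is limited. Under the assumed response rates, a single excluded patient moves the difference by about one point or less (at most 1.5 points over the range shown), against a standard error of 10.5. Taking the illustrative p-value below 0.05 needed three excluded EQW patients and no placebo patients, and nothing in the documents supports that count. SAP 4.2.3.2 treats the goal p-values as exploratory, and the primary MMRM is unaffected. The change is worth making because it is cheap and restores the protocol's rule, not because a conclusion is likely to turn on it.

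**What to change.** Run the HbA1c-goal CMH analysis in the ITT set with ITT denominators, and count every ITT patient without a usable HbA1c at the endpoint as a non-responder. These patients have a stratum for the test, since randomisation is stratified by screening HbA1c (protocol 12.6.9). At minimum, add this run as a sensitivity analysis beside the Evaluable version.

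The imputation analysis can stay in the Evaluable set. If ITT becomes the main analysis, keep the Evaluable non-responder run as supportive, so that the imputation result has a comparator in the same population.

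Align SAP 4.1.3.1, Table 2, 4.2.3.5 and section 5 with the choice. If Evaluable stays as the main set, limit the general rule in 4.1.3.1 to Evaluable patients, and state in section 5 that the baseline-only failure rule of protocol 12.6.3 no longer applies.

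The cost is a population flag in the goal programs, a rerun of the stratified test and a few lines of SAP text. Responder rates may be slightly lower. No new data are needed, and set sizes by arm are already planned for reporting (SAP 4.2.1.1).

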5.9 Withdrawal from study

Patients are at any time free to withdraw from study (investigational product and assessments), without prejudice to further treatment (withdrawal of consent). Such patients will always be asked about the reason(s) and the presence of any AEs. If possible, they will be seen and assessed by an Investigator. Adverse events will be followed up (See Sections 6.4.3 and 6.4.4); and all study drugs should be returned by the patient.

Every effort should be made to conduct all protocol-required procedures to complete the study. Patients may be removed from the study for the following reasons:

1. **Withdrawal by Patient:** Patient wishes to exercise the right to withdraw from the study as stated in the ICF (all patients reserve the right to withdraw from the study without prejudice).
2. **Adverse Event:** Patient experiences an AE that, in the Investigator's opinion, necessitates withdrawal from the investigational product.
3. **Investigator Decision:** Investigator feels it is in the patient's best interest to terminate participation for reasons other than an AE, leading to withdrawal from the investigational product.
4. **Protocol Violation:** Patient is noncompliant with protocol procedures, becomes pregnant, violates study entry criteria, or starts an exclusionary concomitant medication, leading to withdrawal from the investigational product.

5. **Lost to Follow-up:** Patient fails to return for study visits and cannot be reached with reasonable, repeated attempts.
6. **Study Terminated by Sponsor:** AstraZeneca discontinues the study protocol.
7. **Administrative Reason:** The FDA, or other regulatory authority discontinues the study protocol or the clinical study site discontinues participation.
8. **Loss of Glucose Control:** If rescue criteria are met during the controlled assessment period or during the extension period and the Investigator believes it is in the patient's best interest to terminate participation, leading to withdrawal from the investigational product (for specific guidelines see Section 5.5.3 and Section 1.3.1).

Any withdrawal must be fully documented in the patient's source records and recorded on the disposition page of the electronic case report form (eCRF). The documentation must include the reason for the withdrawal and details of any sequelae (followed until symptoms resolve or improve, as appropriate). Withdrawals due to an AE must be documented on both the disposition page and the AE page of the eCRF.

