Section 12.6.3 of the CSP states that the proportion of patients discontinuing the study will be analyzed using a CMH test and logistic regression by visit. However, the team agreed it would be sufficient to summarize withdrawals during the study, which is presented in the disposition summary table. Hence no statistical analyses were planned for this endpoint. In the same section of the CSP, it is stated that the proportion of patients rescued due to failure to maintain glycemic control will be analyzed using a CMH test and logistic regression by visit. However, based on the observed number of patients rescued at Week 24 being low, the team agreed summaries of this endpoint would suffice. By way of a clarification to the CSP, the team also agreed that “number of rescue episodes” should be interpreted as “number of patients rescued”, given a patient is considered rescued after initiation of rescue therapy. Therefore, a summary of the cumulative proportion of patients rescued by visit will be considered sufficient to address this endpoint.

Section 12.6.3 of the CSP states that for MMRM analyses, country will be included as a covariate. However, to align to the approach for the primary endpoint, region will be used instead.

The CSP does not specify BMI percentile as an endpoint, however the study team requested this be included and therefore summaries of observed and change from baseline in BMI percentile will be provided as specified in Section 4.2.3.6 of this SAP.

The CSP does not specify eGFR as an endpoint, nor is it provided by the laboratory. However, the team felt it would provide important information for this study so it will be derived and analyzed as stated in Section 4.2.4.4 of this SAP.

Hypoglycemia analyses are not defined in the CSP. However, the team requested events be classified and summaries be included as defined in Section 4.2.4.7 of this SAP.

Free testosterone in the CSP has been outlined as calculated at Visit 5 (Week 12), Visit 7 (Week 24), Visit 9 (Week 40) and Visit 10 (Week 52). Since this endpoint is calculated using Albumin, total testosterone and SHBG and these parameters are not collected at Week 40, this visit will not be presented in the outputs.

Appendix F of the CSP (Mixed Meal Substudy) lists statistical analyses and summaries will be presented. However, due to an insufficient amount of data being collected for the study, the study team decided no formal analysis will be presented, only summary tables and listings.

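### SAP 4.2.3.5 recognises discontinuation for lack of glycemic control only through an adverse event withdrawal, so a Loss of Glucose Control withdrawal without a qualifying rescue record can be censored and left uncounted

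*SAP*

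**What the plan says.** SAP 3.2 lists the proportion of patients needing rescue because glycemic control failed as a secondary endpoint. SAP 4.2.3.5 reports it through a Kaplan-Meier table and figure of time to rescue and a by-visit table.

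The censoring rule begins: "Patients who are not rescued will be censored at Week 24 visit or last dose of study medication for those who discontinue study treatment". The last-dose date applies "for those who discontinue study treatment for reasons unrelated to lack of glycemic control, as indicated by an adverse event withdrawal that required rescue medication" before the Week 24 visit. For the by-visit table, patients who stop study medication early are counted only up to their last dose, and "Data collected after study treatment discontinuation will be excluded from summaries".

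The event is defined elsewhere. SAP 3.6.4 makes rescue a new concomitant medication carrying the rescue reason on the medication form, and refers to SAP 4.2.1.4 for what counts as new. For patients who do not enter the extension, that class closes 7 days after the last randomized dose. Anything started later is post-treatment.

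Protocol 5.9 lists the reasons for removal. Reason 2 is Adverse Event, an event that in the investigator's opinion "necessitates withdrawal from the investigational product". Reason 8 is Loss of Glucose Control. It applies "If rescue criteria are met during the controlled assessment period or during the extension period" and the investigator judges that stopping is in the patient's interest, leading to withdrawal from the investigational product. The reason goes on the disposition page of the eCRF.

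SAP section 5 drops the protocol's CMH and logistic analyses of rescue, "based on the observed number of patients rescued at Week 24 being low".

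**The concern.** The endpoint is about needing rescue. A reason-8 patient has, by the terms of Protocol 5.9, met the rescue criteria. The SAP rule does not look at that disposition reason. It looks for an adverse event withdrawal, which the protocol treats as a different category.

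The clause is also circular. An adverse event withdrawal that required rescue medication describes a rescued patient, yet the rule applies only to patients who were not rescued. A programmer cannot apply it to a reason-8 patient without guessing.

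Kaplan-Meier assumes that a censored patient has the same future risk as those still followed. A patient stopped because glucose control was lost does not. Censoring at that point is informative and lowers the estimated rescue proportion. With about 22 placebo patients, a single case would show in the curve.

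**Working it through.** The plan states no figure for this endpoint, so there is none to reproduce. The check has two parts.

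**1. Following a reason-8 patient through the rules**

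- *Flagged rescue record while on treatment.* SAP 3.6.4 makes this an event whatever the withdrawal reason. The censoring rule is never reached.
- *Flagged record starting after last dose but within 7 days.* Under SAP 4.2.1.4 this is still a new concomitant medication, so arguably an event. But SAP 4.2.3.5 excludes data after treatment discontinuation from its summaries. The two sections disagree.
- *Therapy starting more than 7 days after last dose, or no flagged record.* This is not a rescue event under SAP 3.6.4. The censoring rule offers two dates for an unrescued patient, the Week 24 visit or last dose, and neither makes the patient an event. Read through the adverse event indicator, the patient is not an adverse event withdrawal and so is censored at last dose. Read through the words about unrelated reasons, last-dose censoring should not apply. What remains is a Week 24 visit that a withdrawn patient may not have. The by-visit table stops counting the patient at last dose.

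The third case is plausible. Dosing is weekly, and Protocol 6.2.1 tells patients to hold a dose due on a visit day until the visit. A patient withdrawn at such a visit before injecting is already about 7 days past the last dose. Protocol 5.5.3 also allows referral to the treating physician, which can delay the start of therapy.

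**2. Weight of one patient**

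Inputs: 77 randomized 5:2 (SAP 1.2 and 1.3), so 77 × 5/7 = 55 exenatide and 77 × 2/7 = 22 placebo. The documents give no counts, so the following are assumptions: k counted rescues at day 100, m reason-8 withdrawals at day 85, and everyone else followed to Week 24.

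- Withdrawals censored: estimate = k / (n − m)
- Withdrawals counted as events: estimate = (k + m) / n

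| Arm | k | m | Censored | Event | Difference (points) |
|---|---|---|---|---|---|
| Placebo, n = 22 | 0 | 1 | 0.0% | 1/22 = 4.5% | 4.5 |
| Placebo | 3 | 1 | 3/21 = 14.3% | 4/22 = 18.2% | 3.9 |
| Placebo | 0 | 3 | 0.0% | 3/22 = 13.6% | 13.6 |
| Placebo | 3 | 3 | 3/19 = 15.8% | 6/22 = 27.3% | 11.5 |
| Exenatide, n = 55 | 0 | 1 | 0.0% | 1/55 = 1.8% | 1.8 |
| Exenatide | 3 | 1 | 3/54 = 5.6% | 4/55 = 7.3% | 1.7 |
| Exenatide | 0 | 3 | 0.0% | 3/55 = 5.5% | 5.5 |
| Exenatide | 3 | 3 | 3/52 = 5.8% | 6/55 = 10.9% | 5.1 |

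If the withdrawals came after all the counted rescues, the difference would be m/n, the top of each range.

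**The case against.** The strongest reply is that the expected patient is counted. Reason 8 requires that rescue criteria were met, and Protocol 5.5.3 says meeting them leads to antihyperglycemic treatment. A flagged record on treatment, and arguably within 7 days of last dose, makes the patient an event. This stands. A reader might infer that every reason-8 patient is censored and never counted. The documents do not support that, since only those without a qualifying record are exposed.

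Second, the phrase about unrelated reasons points away from last-dose censoring for these patients. This also stands as a reading, but it supplies no event and no workable alternative date, so the gap remains.

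Third, some of these patients might carry an adverse event. Protocol 6.4.3.3 makes laboratory deterioration reportable when it is the reason for stopping treatment, but excludes deterioration unequivocally due to disease progression. Even with an adverse event recorded, the disposition reason could still be reason 8. This is not a dependable fallback.

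Fourth, the stakes are limited. Rescue is not in the hierarchy of SAP 4.2.3.2, no between-arm test of the rescue proportion remains, and SAP 4.2.1.1 still reports discontinuation reasons by treatment group. All of that is right. But the disposition table does not feed the rescue proportion or the curve.

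Finally, a reader might infer that the low rescue count cited in SAP section 5 is low because it omits these patients. The SAP does not say how that count was made or whether any reason-8 withdrawal occurred, so the inference is not supported.

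**Conclusion.** The point holds in limited form. SAP 4.2.3.5 uses the wrong indicator for discontinuation due to lack of glycemic control and ignores the protocol category that records it. A reason-8 patient without a qualifying rescue record can be censored at last dose and omitted from the by-visit table, although rescue criteria were met.

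On the assumed counts and timing above, each such patient moves the Week 24 estimate by 3.9 to 4.5 points on placebo and 1.7 to 1.8 points on exenatide. The number of such patients is not stated and could be zero. The direction of any distortion between arms is also unknown: exenatide's advantage would be understated only if these withdrawals are sufficiently more common on placebo, and the documents give no split.

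The primary analysis and the tested secondary endpoints are unaffected. The correction is still worth making, because the rule as written can exclude patients who meet the endpoint's own description.

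**What to change.** Change SAP 4.2.3.5 only:

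- Replace the adverse event clause with the disposition reason Loss of Glucose Control.
- Count a discontinuation for that reason as a needing-rescue event on the discontinuation date, in both the Kaplan-Meier analysis and the by-visit table, unless a rescue event has already been counted. Label the result as rescue or discontinuation for loss of glucose control.
- Censor at last dose only discontinuations for other reasons.
- State whether a rescue medication started after the last dose but within the 7-day window of SAP 4.2.1.4 counts, so that the window and the exclusion of post-discontinuation data agree.

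Leave the definition of rescue therapy in SAP 3.6.4 unchanged, because it governs which data enter the primary analysis.

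The cost is a few sentences and a small programming change. The withdrawal reason is already collected on the disposition page, and SAP 4.2.3.3 already relies on a date of treatment discontinuation. The downside is that the reported proportion may rise slightly and becomes a composite of rescue and glycemic withdrawal. Showing the two components separately would keep that clear.
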